
3. Inclusion and Exclusion Criteria

List the inclusion/exclusion criteria:

Inclusion criteria

PD subjects will be adult men and women diagnosed with idiopathic mild to moderately severe PD defined as modified Hoehn & Yahr Stages I-III (while "On"). PD is defined according to the UK Brain Bank Criteria made at least six months prior to recruitment to the study. PD features include the presence of at least two of the four cardinal clinical manifestations of the disease, which are tremor, rigidity, bradykinesia, and disturbances of posture or gait, without any other known or suspected cause of Parkinsonism. Subjects should be stabilized on PD medication for at least 3 months before enrollment into the study. Subjects' PD drug prescriptions will not be altered nor withheld during the study, i.e., they will be tested while "On." The patient will have signed informed consent. Subjects who do not have PD (i.e., healthy or have other medical conditions such as TBI, stroke, or other syndromes in which inflammation plays a role in the condition will also be recruited as control subjects. This will allow us to estimate whether these other conditions show similar or unique inflammatory profile.

Exclusion criteria

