Subjects will be excluded if they had previous brain surgery or other severe neurological problems – intracerebral hemorrhage, traumatic brain injury, central nervous system malignancy, active CNS infection, significant stroke, Alzheimer disease or any type of implanted stimulator including but not limited to Deep Brain Stimulator (DBS) or pacemaker. All subjects must be without evidence of dementia, defined as a score > 24 the Mini-Mental State Examination and able to understand test instructions. Subjects must not have functional blindness (inability to participate in gait and visuomotor assessments) or lower limb amputation higher than the forefoot or any orthopedic problem that precludes performance of physical tests. Allergic to niacin. Significant cardiac, pulmonary, hepatic, gastrointestinal, or renal disease (e.g., New York Heart Association Class III or IV congestive heart failure; endocarditis; pulmonary insufficiency symptomatic at rest or with mild physical exertion; acute or chronic hepatitis; renal failure requiring dialysis; second and third degree AV block or sick sinus syndrome), or diabetes are also exclusionary factors.

4. Number of Subjects/Records/Samples Collected

Indicate the total number of subjects to be accrued/records reviewed/samples collected across all sites:

100

5. Recruitment Methods

Describe when, where, and how potential subjects will be recruited:

VA clinic (including medical records), word of mouth.

6. Procedures Involved

a. *Describe the procedures involved to include those procedures that are standard evaluation and/or care and those that are solely for research purposes:*

Standard procedures: basic physical examination for strength, speed, coordination, tremor, flexibility, rigidity and reaction time

Research procedures: questionnaire and tests to document health and cognitive status, blood, urine and spinal fluid samples, over-the-counter (non-prescription) vitamin B3 supplementation

b. Describe and explain the study design: Pre-post repeated measures placebo-controlled study

c. Describe the procedures performed to lessen the probability or magnitude of risks: Use of slow-release supplement to minimize potential skin itching

d. Describe the duration of an individual subject's participation in the study and the time involved: 6 months supplement study with a pre and post test, each lasting about 1 to 1.5 hr.

7. Data and Specimen Management

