
a. Describe the data analysis plan, including any statistical procedures: We will use the Unified Parkinson's Disease Rating Scale (UPDRS) III (Motor Section) as the primary pre- and post-treatment outcome assessment that is recommended for PD studies. Significant changes in outcome measures will be determined by performing a Mixed model analysis of variance, with Groups as the independent factor and Time as the repeated factor.
	 N/A												

b. When applicable, provide a power analysis: Based on the preliminary data using unpaired simple effects analyses, the minimum number of subjects needed per group to detect a statistical significance @ $p = .05$, 2-tailed and 80% power of detection are as follows:
 
  
 Outcome measures	Effect size (based on Cohen's d)	#	
   
 Subjects/group			
 
 UPDRS motor	1.46	14	
 
 Sleep efficiency (pilot data)	0.97	8	
  
 
The sample sizes are based on a large effect size, i.e., a grossly observable and clinically meaningful treatment effect. We have demonstrated that this is a reasonable expectation based on the actual effect sizes of the human preliminary data that we have shown. We used simple effects analyses as the basis for the sample size calculations because any sample size calculations based on the full design would require knowledge of the intra-class correlation across the treatments, as well as the carry-over, group, and period effects.
 
Correlation statistics. Based on the preliminary data's correlation coefficients (r) obtained via simple linear independent correlation tests comparing the variables versus disease severity (UPDRS motor section), the minimum number of subjects needed per group to detect a statistical significance @ $p = .05$, and 80% are as follows:
	Outcome measures	Effect size (based on Cohen's d)	#	Subjects/group			UPDRS motor	1.46	14	Sleep efficiency (pilot data)	0.97	8	 N/A
Outcome measures	Effect size (based on Cohen's d)	#											
Subjects/group													
UPDRS motor	1.46	14											
Sleep efficiency (pilot data)	0.97	8											

Outcome measures GPR109A levels Total Sleep Time Time to Fall Asleep Sleep Efficiency	r 0.59 -0.57 0.79 -0.73	# Subjects/group 20 18 8 10	

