
Based on the simple effects and correlation power analyses above, we propose to collect 30 PD subjects per group (total 60) to account for potential subject dropouts, experimental/data corruption and/or an unexpected increase in the variability of the data. We plan to recruit about 100 subjects to take into account potential drop-outs and an unexpected increase in the variability of the data which impacts the estimated statistical power.
			
c. Describe how data and specimens will be handled:			 N/A
i. What information will be included in that data or associated with the specimens?			
	Please refer to 6a above. All data will be coded.		
ii. Where and how data and/or specimens will be stored?			
	Specimens: Core lab. Data: Secured computer. ICD will be stored in a locked cabinet. NOTE: All data including specimens will be coded.		
iii. How long will the data and/or specimens be stored?			
	Indefinitely		
iv. Who will have access to the data or specimens?			
	Research team		
v. Who is responsible for receipt or transmission of the data and/or specimens?			
	[name] (PI)		
vi. How will data and/or specimens be transported?			
	Manually		

8. Provisions to Monitor the Data to Ensure the Safety of Subjects

This study involves no more than minimal risk study and this section is not required. **N/A**

The plan might include establishing a data monitoring committee and a plan for reporting data monitoring committee findings to the IRB and the sponsor.

a. *Describe the plan to periodically evaluate the data collected regarding both harms and benefits to determine whether subjects remain safe.*

Subjects will be contacted the day after their pre- and post-test participation in the study to make sure that they did not experience unexpected or severe reactions to the vitamin supplement and optional lumbar puncture. A log will be kept to document the contact and relevant information from the subject. Subjects will also be given a 24-hour hotline to report any adverse event that they think is related to the study.

b. *Describe what data are reviewed, including safety data, untoward events, and efficacy data.*

Safety and untoward events related to the vitamin supplement and optional lumbar puncture will be reviewed.

c. *Describe how the safety information will be collected (e.g., with case report forms, at study visits, by telephone calls with participants).*

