Safety information will be collected by telephone calls or emails with the participants.

d. *Describe the frequency of data collection, including when safety data collection starts.*

Data will be collected by the researchers at baseline and the end of the study. Subjects will be instructed to contact the researchers as soon as possible if they experience any adverse events that they think is related to the study.

e. *Describe who will review the data.*

[name] will be the main person to review the data. He will consult with [name] or [name] if needed.

f. *Describe the frequency or periodicity of review of cumulative data.*

Cumulative data will be reviewed every month to ensure adherence to the approved protocol.

g. *Describe any conditions that trigger an immediate suspension of the research.*

If a subject reports an unexpected adverse event, the study will be suspended. The study will resume if it is determined that the event is unrelated to the study.

9. Withdrawal of Subjects

N/A

a. If applicable, describe anticipated circumstances under which subjects will be withdrawn from the research without their consent.
 
Click here to enter text.
	 N/A

b. If applicable, describe any procedures for orderly termination.
 
Click here to enter text.
	 N/A

c. If applicable, describe procedures that will be followed when subjects withdraw from the research, including partial withdrawal from procedures with continued data collection.
 
A subject who withdraws from the study on their own accord will be replaced by another. A subject who partially withdraws from procedures will remain in the study as long as they continue taking the supplement.
	 N/A

10. Risks to Subjects

a. List the reasonably foreseeable risks.

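### If niacin or placebo is allocated at random, adjusting 6-month UPDRS III for its baseline is usually more precise than the planned Group × Time (change-score) test, at a cost of one degree of freedom

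*Combined protocol and SAP*

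**What the plan says.** All references are to the combined protocol and SAP.

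- **Outcome (7a).** UPDRS III serves "as the primary pre- and post-treatment outcome assessment". Sections 6d and 8d give one test at the start and one at the end of 6 months.
- **Analysis (7a).** The method is "Mixed model analysis of variance, with Groups as the independent factor and Time as the repeated factor". No baseline covariate is listed, and no term (Groups, Time or their interaction) is named as the one that decides the trial.
- **Design (6b).** The study is a "Pre-post repeated measures placebo-controlled study". Random allocation is not mentioned there or elsewhere.
- **Groups (3).** Non-PD controls are also recruited, to estimate "whether these other conditions show similar or unique inflammatory profile". Section 7a does not say which groups enter the UPDRS III comparison.
- **Sample size (7b).** The calculation is "Based on the preliminary data using unpaired simple effects analyses", with d = 1.46 and 14 per group for UPDRS motor. The reason given is that sizing the full design "would require knowledge of the intra-class correlation across the treatments, as well as the carry-over, group, and period effects". The plan then settles on 30 PD subjects per group.

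**The concern.** The natural treatment test in the planned model is Group × Time. With two time points it subtracts the whole baseline score from the 6-month score. That is the best use of the baseline only when the regression slope of post on pre is 1. At a lower slope, the subtraction carries baseline noise into the comparison. An ANCOVA estimates the slope instead of fixing it at 1.

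The stake is precision, not validity. Under random allocation both tests are unbiased for the same treatment effect, and the trial already collects the baseline score. Section 7b also declines to size the full design because the correlation is unknown, and Group × Time is the test that depends more heavily on that unknown.

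**Working it through.** **Inputs from the documents.** Two-sided .05, 80% power, d = 1.46 and 14 per group for UPDRS motor, 30 per group planned (7b); one pre-test and one post-test (6d, 8d).

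**Assumed, because the documents do not give them.** Pre-post correlation ρ; ratio k of post SD to pre SD (k = 1 unless stated); random 1:1 allocation; complete data; effects expressed in SDs of a single score.

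**1. The plan's own figure.** An unpaired two-sample t-test at d = 1.46 needs 9 per group for 80% power (8 by the normal approximation), not 14; 14 per group gives 96%. This mismatch is a separate matter, and nothing below depends on it.

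**2. Group × Time is the change-score test.** In simulated data sets of 30 per group, the interaction F equalled the squared t on change scores, with a largest difference of 4 × 10⁻¹⁴.

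**3. Variances, in units of pre-test variance × 2/n.**
- Change score: 1 + k² − 2ρk
- ANCOVA: k²(1 − ρ²) × [1 + 1/(2n − 4)]

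Without the bracket, change minus ANCOVA is (1 − ρk)², which is never negative. The bracket is the cost of estimating the slope. At n = 30 it is 1 + 1/56 = 1.018, so ANCOVA can lose at most about 2%.

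**4. Variance ratio, ANCOVA to change, at 30 per group.**

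| ρ | k = 1 | k = 1.2 |
|---|---|---|
| 0.5 | 0.75 × 1.018 / 1.00 = 0.763 | 1.08 × 1.018 / 1.24 = 0.887 |
| 0.7 | 0.51 × 1.018 / 0.60 = 0.865 | 0.734 × 1.018 / 0.76 = 0.984 |
| 0.8 | 0.36 × 1.018 / 0.40 = 0.916 | 0.518 × 1.018 / 0.52 = 1.015 |

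The reductions are 24%/13%/8% with equal SDs, and 11%/2%/none (a 1.5% loss) at k = 1.2. With k below 1 the gain is larger: at k = 0.8 and ρ = 0.5 the ratio is 0.48 × 1.018 / 0.84 = 0.58. Simulation of 20,000 randomised trials at each of ρ = 0.5, 0.7 and 0.9 with k = 1 gave ratios of 0.78, 0.87 and 0.96 (theory 0.76, 0.87, 0.97), with both estimates unbiased.

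**5. Difference detectable with 80% power, 30 per group, k = 1.** The unpaired test detects 0.7356 SD (noncentral t, 58 df). Multiply by √[2(1 − ρ)] for Group × Time and by √[(1 − ρ²) × 1.018] for ANCOVA. Moving to 57 df changes the critical t only from 2.0017 to 2.0025.

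| ρ | Group × Time | ANCOVA |
|---|---|---|
| 0.3 | 0.870 | 0.708 |
| 0.5 | 0.736 | 0.643 |
| 0.7 | 0.570 | 0.530 |
| 0.8 | 0.465 | 0.445 |
| 0.9 | 0.329 | 0.324 |

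For an illustrative true effect of 0.5 SD, power rises from 48% to 59% at ρ = 0.5 and from 69% to 75% at ρ = 0.7.

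**6. At the plan's effect.** With d = 1.46 in single-score SDs and k = 1, Group × Time at ρ = 0 has noncentrality (1.46/√2) × √(30/2) = 4.0 and power of 97.6%. Any positive ρ gives more; at ρ = 0.5 it is 99.98%.

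**The case against.** The strongest reply is that this is a choice between two valid tests in a trial with power to spare at its own effect size. That stands, and it limits the point to a conditional gain in precision.

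Three further objections also stand in part:

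- **Equal SDs.** The 24%/13%/8% figures need equal pre and post SDs, which the documents do not give. With equal SDs, ANCOVA keeps its edge up to a correlation of about 0.96, and a reader might take that as a general threshold. It is not one: at k = 1.2 the edge has already gone at ρ = 0.8. The general result is the bound on the loss, about 2% at 30 per group.
- **Dropout.** A reader might infer that attrition will cut the analysed number and make the gain larger. The documents give no dropout rate. Section 7b says "we propose to collect 30 PD subjects per group (total 60) to account for potential subject dropouts", and 9c says "A subject who withdraws from the study on their own accord will be replaced by another". No smaller analysed number can be derived from the plan, so none is claimed here.
- **Carry-over and period effects.** A reader might infer from 7b that a crossover was intended or that the analysis is wrong. Section 6 describes one 6-month comparison, and section 11 adds only an optional assessment after all subjects receive niacin. The 7b sentence explains why those effects were left out of the sizing. It should be reconciled with 6b, but it changes no result.

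It may also be said that allocation is unstated, so ANCOVA cannot simply be prescribed. That is correct, and the fix is conditional for this reason. In non-randomised groups, including any PD versus non-PD comparison, baseline adjustment is not a free gain.

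**Conclusion.** The point holds as a conditional improvement in precision. If niacin or placebo is allocated at random, ANCOVA on baseline UPDRS III is at least as precise as Group × Time, apart from a slope cost of at most about 2% of variance at 30 per group. With equal SDs and correlations of 0.5 to 0.8 the variance saving is 24% down to 8%; by a correlation of 0.9 it is negligible (0.329 against 0.324 SD). It is smaller if scores spread out over 6 months and larger if they narrow.

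A reader might conclude that the planned test is invalid or the trial underpowered. The documents support neither: the change-score test is valid, and at d = 1.46, with equal SDs and a non-negative correlation, power is at least 97.6%. That figure takes d in single-score SDs; 7b does not say which contrast or SD produced it. The benefit is for true effects well below 1.46 and for the width of the confidence interval.

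**What to change.** 1. **Settle the condition.** State in 6b whether allocation to niacin or placebo is random.
2. **If it is random, write in 7a:** the primary test is the niacin-versus-placebo term, among PD subjects, in an ANCOVA of 6-month UPDRS III with baseline UPDRS III as covariate, two-sided at .05, reported with its 95% confidence interval.
3. **If it is not random, write in 7a:** the deciding term is Group × Time among PD subjects.
4. **Optional, in 7b:** give the detectable difference for the chosen test at 30 per group over a stated range of correlations (for example 0.3 to 0.8) and SD ratios, and reconcile the carry-over and period wording with 6b.

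The cost is one residual degree of freedom (58 to 57 at 30 per group) and a few sentences. No new data are needed, because baseline UPDRS III is already collected.

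### Section 7b: neither row of the Cohen's d table meets its stated two-tailed 80% power (d = 0.97 needs 18 per group, not 8; d = 1.46 needs 9, not 14)

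*Combined protocol and SAP*

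**What the plan says.** Section 7b sets out the conditions for its first table: "Based on the preliminary data using unpaired simple effects analyses, the minimum number of subjects needed per group", at p = .05, "2-tailed and 80% power of detection are as follows". The table then has two rows: "UPDRS motor 1.46 14" and "Sleep efficiency (pilot data) 0.97 8". Section 7a names UPDRS III (motor) as the primary outcome.

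A second table, for correlations with UPDRS motor score, is introduced by "significance @ $p = .05$, and 80% are as follows", with no statement of one or two tails. For GPR109A level, total sleep time, time to fall asleep and sleep efficiency, in that order, it lists "r 0.59 -0.57 0.79 -0.73" against "Subjects/group 20 18 8 10".

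The section then sizes the trial from both tables: "Based on the simple effects and correlation power analyses above, we propose to collect 30 PD subjects per group", 60 in total, with about 100 to be recruited.

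**The concern.** At a fixed alpha, power and test, a larger effect needs fewer subjects. The first table runs the other way: 14 for the larger effect and 8 for the smaller. The correlation table has one similar inversion, with 20 for |r| = 0.59 and 18 for |r| = 0.57.

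Two things are at stake. First, the power claim for sleep efficiency may be badly overstated. Second, if the rows were transposed when the table was typed, the pilot effect for the primary outcome would be 0.97 rather than 1.46, and the printed 14 would fall short of 80% power. Section 7b defends the design by the size of its pilot effects, so it matters which effect belongs to UPDRS motor.

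**Working it through.** **Inputs, all from Section 7b:** unpaired groups of equal size; alpha 0.05, two-tailed; power 80%; d = 1.46 with n = 14; d = 0.97 with n = 8; planned n = 30 per group.

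**Quick check by normal approximation.** n per group = 2(1.960 + 0.842)²/d² = 15.70/d².
- d = 1.46: 15.70/2.132 = 7.4, so 8.
- d = 0.97: 15.70/0.941 = 16.7, so 17.

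**Exact two-sample t-test.** Degrees of freedom are 2n − 2 and the noncentrality is d√(n/2). Power is the probability that a noncentral t falls beyond ± the critical value. For example, at d = 0.97 and n = 8 the noncentrality is 0.97 × 2 = 1.94, the critical value on 14 df is 2.145, and power is 43.9%.

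| n per group | d = 1.46, two-sided | d = 0.97, two-sided |
|---|---|---|
| 8 | 77.5% | **43.9%** (as printed) |
| 9 | 82.8% (minimum) | 49.0% |
| 14 | **96.1%** (as printed) | 69.5% |
| 17 | 98.5% | 78.3% |
| 18 | 98.9% | 80.7% (minimum) |
| 30 | 99.98% | 95.9% |

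The minimums are therefore 9 and 18, against 14 and 8 in the plan. With 80% power, 8 per group detects d = 1.51 and 14 per group detects d = 1.10.

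**Attempts to reproduce 14 and 8 as printed:**
- n values swapped, two-sided: 77.5% (d = 1.46, n = 8) and 69.5% (d = 0.97, n = 14). Both miss 80%.
- One-sided, unpaired: minimums 7 (82.3%) and 14 (80.3%; 13 gives 77.6%).
- Paired: minimums 6 and 11 two-sided, 5 and 9 one-sided.
- Two-sided at 95% power: 14 and 29. This matches the first row only.

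None of these gives both rows. The closest is a row swap combined with a one-sided calculation (14 for d = 0.97; 7, against a printed 8, for d = 1.46). That contradicts the stated two tails.

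**Correlation table.** Power was simulated under bivariate normality using the usual t-test of r. The last two columns give the minimum n from simulation, with the Fisher-z value, ((z_α + 0.842)/atanh r)² + 3, in brackets.

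| \|r\| | printed n | power at that n, two-sided / one-sided | two-sided minimum | one-sided minimum |
|---|---|---|---|---|
| 0.59 | 20 | 82% / 89% | 20 (20.1) | 16 (16.5) |
| 0.57 | 18 | 73% / 83% | 21 (21.7) | 17 (17.7) |
| 0.79 | 8 | 73% / 84% | 9, borderline (9.8) | 8 (8.4) |
| 0.73 | 10 | 74% / 84% | 12 (12.1) | 10 (10.2) |

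The 20 is a two-sided minimum. The 18, 8 and 10 reach 80% only one-sided.

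**Planned size.** At 30 per group, two-sided, power is 95.9% at d = 0.97 and 99.98% at d = 1.46. It is 80% at d = 0.736. For the four correlations at n = 30 it is about 95%, 93%, 99.98% and 99.8%. If 12 of 30 were lost in each group, the remaining 18 would still give 80.7% at d = 0.97.

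**The case against.** The strongest reply is that no design decision changes. The plan is 30 per group, which exceeds every printed figure and every corrected one, and nobody proposes to run 8 per group. The primary-outcome row errs on the safe side, and sleep efficiency is not named in the objectives (Section 1) or the procedures (Section 6a). This stands. It limits the point to a correction of the justification, not a challenge to the sample size.

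A second reply is that transposition is conjecture. It needs two mistakes together and still does not give 8, and the table does label 1.46 as UPDRS motor. This also stands in part: transposition is a question for the sponsor, not a finding. But a table that fails on its own terms is weak evidence that its labels are right, so the question has to be asked.

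A third reply is that the correlation figures depend on the power model. With the predictor treated as fixed (noncentrality √n·r/√(1 − r²)), two-sided power is 85.7% for 0.79 at n = 8 and 84.0% for 0.73 at n = 10, and both are then two-sided minimums. That is arithmetically right. However, it conditions on a predictor that here is measured, not set. It also gives 17 and 19 for 0.59 and 0.57, not the printed 20 and 18. It cannot explain the inversion between those two rows.

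**Conclusion.** The concern holds. Under the conditions that Section 7b states, both d rows are wrong, in opposite directions: the sleep-efficiency minimum is understated (8 for 18, with 44% power instead of 80%) and the UPDRS motor minimum is overstated (14 for 9). Swapping the n values does not cure this. The correlation table is a lesser fault: sidedness is missing, one pair is out of order, and no single convention examined gives all four entries.

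The planned 30 per group is adequate under either row order. If the effects were transposed, UPDRS motor would have d = 0.97; the printed 14 would give 70%, but 30 gives 96%.

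These results assume a two-sample t-test with equal groups, true effects equal to the printed pilot effects, and, for the correlations, bivariate normality. This should be fixed, since the sample size is expressly based on these tables.

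**What to change.** 1. Check the effect sizes, row order and sidedness against the pilot data and the source calculation.
2. If the printed effects are right, restate the minimums as UPDRS motor (1.46) 9 per group and sleep efficiency (0.97) 18 per group. If the effects were transposed, restate them as UPDRS motor (0.97) 18 and sleep efficiency (1.46) 9.
3. State the sidedness and power method of the correlation table and recompute all four rows on that basis. Two-sided, the minimums are 20–21, 21–22, 9–10 and 12–13 in the printed order; each range runs from the simulated bivariate-normal value to the Fisher-z value rounded up.
4. Add one sentence, for example: with 30 evaluable subjects per group, a two-sided unpaired t-test at 0.05 has 80% power for a standardised difference of about 0.74.

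The cost is one look at the source calculation, two small table corrections and one added sentence. The 30 per group stays, and no extra patients are needed.

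### Supplement harms that subjects do not link to the study are likely to be under-recorded over 6 months, and the protocol contradicts itself on itching (minor)

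*Combined protocol and SAP*

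**What the plan says.** The relevant text is in Sections 6 and 8 to 11 of the combined protocol and SAP.

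- **Exposure (6d, 11):** 250 mg daily for 6 months, with one pre-test and one post-test of about 1 to 1.5 hours each.
- **Scheduled contact (8a):** "Subjects will be contacted the day after their pre- and post-test participation in the study", with the purpose "to make sure that they did not experience unexpected or severe reactions to the vitamin supplement and optional lumbar puncture". A log of each contact is kept.
- **Self-report (8a, 8d):** "Subjects will also be given a 24-hour hotline to report any adverse event that they think is related to the study". 8d asks subjects to contact the researchers promptly "if they experience any adverse events that they think is related to the study".
- **Scope of review (8b):** "Safety and untoward events related to the vitamin supplement and optional lumbar puncture will be reviewed".
- **Mode and timing (8c, 8d):** "Safety information will be collected by telephone calls or emails with the participants"; "Data will be collected by the researchers at baseline and the end of the study".
- **Monthly review (8f):** directed at protocol adherence; it adds no contact with subjects.
- **Suspension (8g):** a reported unexpected adverse event suspends the study. The only stated condition for restarting is that the event proves unrelated.
- **Withdrawal (9c):** subjects who leave are replaced; no closing question about harms is described.
- **Itching:** 6c chooses a slow-release product to limit it. 10a lists only blood-draw and lumbar-puncture risks. Section 11 states that the dose has no side effects.

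**The concern.** Two separate matters arise.

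The first is ascertainment. If the supplement starts at the pre-test, the first contact covers about a day of dosing at most. The second comes after dosing ends and is aimed at unexpected or severe reactions. In between, a harm reaches the record only if the subject both suspects the study and takes the trouble to report it. That filter matters because a subject with Parkinson's disease may put a new symptom down to the disease or to other medication. A low or zero count of reactions would then say little about tolerability.

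The second is a conflict in the text. Itching is anticipated in one section, absent from the risk list in another, and excluded by implication in a third. Staff handling a report of itching would not know whether it is expected, and 8g makes that the deciding question for suspending the trial.

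**Working it through.** The plan gives no figure for adverse-event ascertainment, so there is nothing to reproduce. The main check is to follow each kind of event through the stated rules.

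| Event | Scheduled contact (8a) | Self-report (8a, 8d) | Review |
|---|---|---|---|
| Severe or unexpected reaction | Yes; the post-test contact may pick it up late | Yes, if attributed | 8b if related; 8g if unexpected |
| Mild, attributed by the subject | Not asked about | Yes, at any severity, but passive | 8b |
| Not attributed by the subject | Only if it is raised as a severe or unexpected reaction | None | Only if reported and treated as unexpected (8g) |

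The second row loses events because nobody asks. The third loses them because the wording leaves them out. The Section 6a procedures include a "questionnaire and tests to document health and cognitive status", which might bring some events to light, but it is not described as asking about adverse events, and 8c does not name it as a source.

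**Itching under 8g.** Step 1: 10a and 11 give no supplement risk, so on their text itching is unexpected. Step 2: 8g then suspends the study. Step 3: the only stated way to resume is a finding that the event is unrelated. Step 4: itching caused by niacin is related, so no route to resume is stated. If 6c is taken as making itching expected, step 1 fails and nothing is triggered. The protocol does not say which reading applies.

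**Illustration of what a zero count would mean.** Inputs: n = 30 on niacin (Section 7b, 30 subjects with Parkinson's disease per group, taking one group as the niacin group). The true risk p and the fraction of events recorded f are assumptions, because the documents give neither. Subjects are treated as independent.

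The upper one-sided 95% limit on the true rate after zero records is [1 − 0.05^(1/n)] / f. With n = 30 and f = 1 this is 1 − 0.05^(1/30) = 9.5%. Dividing by f = 0.50 gives 19.0%, and by f = 0.25 gives 38.0%.

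The chance that no event is recorded is (1 − p·f)^n. With n = 30:

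| p | f = 1 | f = 0.50 | f = 0.25 |
|---|---|---|---|
| 5% | 21% | 47% | 69% |
| 10% | 4% | 21% | 47% |
| 20% | 0.1% | 4% | 21% |

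For example, with p = 0.10 and f = 0.25: (1 − 0.025)^30 = 0.468.

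An upper case of n = 50 is half of the roughly 100 to be recruited, who may include controls without Parkinson's disease. The limits are then 5.8%, 11.6% and 23.3%, and at p = 10% the chances of no record are 0.5%, 8% and 28%.

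The 9.5% and 5.8% limits come from sample size alone. Only the movement across the columns reflects incomplete recording.

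**The case against.** The strongest reply is that this is a low-dose, over-the-counter supplement in a study classed as minimal risk, and that Section 8 is marked as not required. The sponsor nevertheless wrote a monitoring plan with a hotline, a contact log and a suspension rule. Safety is not among the objectives in Section 1, and nothing says a zero count will be used to support the statement in Section 11. The values of p and f above are assumed. All of this stands, and it keeps the point minor. It does not remove the attribution filter or the conflict over itching, both of which are in the written rules.

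A reader might infer more than the documents support:

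- *That mild reactions cannot be reported.* They can: the hotline and the 8d instruction have no severity limit. The loss is from passive reporting, not from a closed channel.
- *That unattributed events are never reviewed.* 8g sets no relatedness condition before it acts, so a reported unexpected event is assessed for relatedness whatever the subject thought.
- *That 8d also restricts collection to unexpected or severe reactions.* That limit appears only in 8a.
- *That subjects were not told about itching.* Section 13 says consent covers risks, and the consent pages are not in the available text.
- *That the itching conflict causes under-recording.* It is a separate inconsistency.

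A further fair objection is that itching questions put before motor scoring could reveal allocation in a placebo-controlled design. The fix has to allow for this.

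**Conclusion.** The point holds as a minor one. Followed as written, the rules leave attributed mild reactions to passive reporting and give unattributed events no self-report route, with 8g as their only stated path to review. Under-recording is likely, and its direction is downward. Its size cannot be derived from the documents: the percentages above show only how quickly a zero count loses meaning under assumed recording fractions. The UPDRS motor analysis in Section 7a is unaffected, and no between-group safety comparison is planned, so a reader should not infer bias in the trial's stated results.

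The itching conflict between 6c and Sections 10a and 11 stands whatever the event rate. The suspension with no stated way back follows only if itching is read as unexpected, which the text permits but does not require.

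**What to change.** 1. **Ask once, systematically.** At the existing post-test visit, after UPDRS scoring is complete and before any real niacin is given, put the same cause-neutral adverse-event checklist to both groups, covering the whole supplementation period. Do the same at withdrawal where the subject can be reached. Add this to 8c.
2. **Remove the filters.** In 8a and 8d, ask subjects to report any adverse event whatever they think caused it. In 8a, drop the restriction of the scheduled contacts to unexpected or severe reactions. In 8b, review all reported events.
3. **Resolve the conflict on itching.** List skin itching in 10a as a foreseeable supplement risk, delete the sentence in Section 11 that denies side effects, and state in 8g that mild itching is expected and does not by itself suspend the study. The exemption should cover mild itching only.

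The cost is a few minutes per subject at a visit that already takes 1 to 1.5 hours, somewhat more events to review, and a less favourable safety statement. Wider reporting may also bring more unexpected events under the 8g suspension rule. No visits or interim calls are added. Recall over 6 months is imperfect, especially for mild passing events, so the checklist reduces the under-count without removing it. If it raised recording from 25% to 50% (an assumption), the chance of no record at a 10% risk with n = 30 would fall from 47% to 21%.
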